9.4. Data Sources

Several European EHR databases will be used to evaluate dulaglutide uptake, volume and data availability. The following databases have been selected for further consideration based on data availability and completeness:

- France: IMS Disease Analyzer (French DA),
- Germany: IMS Disease Analyzer (German DA),
- Spain: The Information System for the Development of Research in Primary Care (SIDIAP),
- Sweden: National Health registers that is, National patient register (NPR) and the Swedish prescribed drug register (SPDR),
- United Kingdom: Clinical Practice Research Datalink (CPRD).

9.4.1. Disease Analyzer in France and Germany

The IMS Disease Analyzer (DA) is a longitudinal patient database providing information from continuing physician and patient interactions on consultations, diagnoses and treatments. This database is available in France and Germany. Anonymous data are collected continuously through the medical software, allowing longitudinal follow-up of all the different visits of the same patient consulting the same general practitioner (GP) in the panel. The collected data include administrative (for example, insurance scheme, socioeconomic status), demographic (for example, age, gender, region), anthropometric (for example, height, weight, body mass index [BMI]), clinical (signs, symptoms and diagnoses according to ICD-10 classification), laboratory (lab results reported by the physicians) and therapeutic (EPHMRA/ATC class, molecule / brand name, dosage, route of administration) information. An update of the database is done monthly with a lag time of 6 weeks.

Comparisons with external data sources (for example, data from statutory health insurances) underline the validity and representativeness of the German DA in pharmacoepidemiological and pharmaco-economic studies (7).

The DA is currently used by the European Medicines Agency (EMA) as one of its resources for answering research questions.

DA in France:

The data collection is based on five different EHR applications used by 1200 GPs. The French database is representative in terms of GP distribution, patient profile, age group, and sex. It allows for a longitudinal follow-up of all the different visits of the same patient consulting the same GP in the panel. Due to the role of GPs as the first point of care in France, the loyalty of patients to GPs is very high and each GP provides a continuous follow-up of patients.

DA in Germany:

The German DA is based on patient records continuously collected from 2400 computerised practices (including 1400 GPs and 1000 specialists), using three different EHR application. The sample is designed to be representative of Germany (7).

9.4.2. SIDIAP in Spain

The SIDIAP database contains information from 274 primary care centres in Catalonia, Spain, with a source population of 5.5 million patients which encompasses 80% of the total Catalan population. The SIDIAP aims to register all health information with research value in an anonymised database for every patient.

The Primary Care e-records (eCAP) database which contains information on primary care since 2000 is the basis of the source population in SIDIAP. Various external data sources can be linked to eCAP as required to provide a more complete picture of the cohort profile. In this study, it is proposed to use eCAP, Catalan Health Service Database (SIAP), Pharmacy Official Invoice Database, Primary Care Lab Database, and CMBD-AH to capture the parameters required in this study.

Table 9.4.2-1. Collectable Data in the Databases Linkable to SIDIAP

Variables	Source	Years available
Clinical (GP visits, referrals, vaccines, smoking, drinking, body mass index, blood pressure, spirometry, ICD-10 codes, etc.)	eCAP (Primary Care e-records)	>2000
Sociodemographics (date of birth, gender, country of origin)	SIAP (Catalan Health Service Database)	>2000
Drugs dispensed in community pharmacies	Pharmacy Official Invoice Database (subsidised drugs)	>2005
Lab tests (creatinine, HbA1c, et cetera.)	Primary Care Lab Database	>2006

Abbreviations: GP= general practitioner; HbA1c= haemoglobin A1c; ICD-10= International classification of disease, 10th version.

9.4.3. NPR and SPDR in Sweden

Swedish data combine data from the NPR, covering all specialist and hospital care in Sweden, and the SPDR, covering all drugs dispensed at pharmacies in Sweden. The national registers are

updated at least quarterly. These longitudinal data enable to find out comorbidities and historical clinical information on the subjects treated for their T2DM in a hospital, as well as drug prescription details (both primary and secondary care). Prescriptions are not formally linked to an ICD-10 code, but clinical input could provide rationale for linking prescriptions and diagnosis made in secondary care. However, information on patient anthropometric data (height, weight, BMI) are not available through the databases, nor are lab results and clinical measurements such as HbA1c, blood pressure and blood lipid levels.

9.4.4. CPRD in the UK

The CPRD is a well-validated database with high-quality information on medications, laboratory data, specialist referral and diagnoses assigned by primary care clinicians. It is jointly funded by the NHS National Institute for Health Research (NIHR) and the Medicines and Healthcare products Regulatory Agency (MHRA).

The CPRD has one of the world's largest computerised databases of anonymised longitudinal medical records from primary care that is linked with other healthcare data in the UK. Currently, data are being collected on approximately 5 million active patients from around 683 primary care practices throughout the UK (about 8% of the universe).

9.4.5. Summary of Data Sources

The following table (Table 9.4.5-1) presents the expected data which could be provided from local databases.

Table 9.4.5-1. Data Availability per Database / Country

Data availability per country (local database)	France (FR-DA)	Germany (DE-DA)	Spain (SIDIAP)	Sweden (NPR and SPDR)	The UK (CPRD)
Demographics (age, gender)	Yes	Yes	Yes	Yes	Yes
Clinical parameters (height, weight, BMI,)	Yes	Yes	Yes	No	Yes
Physiological status: pregnancy breastfeeding women	Very limited	Very limited	Very limited	Very limited	Very limited
Date of consultation	Yes	Yes	Yes	Yes	Yes
Diagnosis	Yes ICD-10 codes	Yes ICD-10 codes	Yes ICD-10 codes	Yes ICD-10 codes	Yes READ codes
Prescribed drug characteristics (name, form, package, classification code)	Yes (ATC/EphMRA codes)	Yes (ATC/EphMRA codes)	Yes (ATC codes)	Yes (ATC codes)	Yes (associated medcodes)
Dosage	Yes	Yes	Yes	Yes	Yes
Duration exposure	Yes	Yes	Yes	Yes	Yes

Co-prescriptions	Yes	Yes	Yes	Yes	Yes
Treatment history	Yes	Yes	Yes	Yes	Yes
Biological test (HbA1c, cholesterol level, creatinine, ..)	Yes	Yes	Yes	No	Yes

Abbreviations: CPRD= Clinical Practice Research Datalink; DE-DA= Deutschland Disease Analyzer; FR-DA= France Disease Analyzer; HbA1c= haemoglobin A1c; ICD-10= International classification of disease, 10th version; NPR= National Prescription Registry; SIDIAP= The Information System for the Development of Research in Primary Care; SPDR= Swedish prescribed drug register.

9.5. Study Size

9.5.1. Sampling

The real number of eligible patients included in the dulaglutide group will depend on the uptake and volume of the drug in each country.

The sample size formula, based on the normal approximation to the binomial distribution, for calculation of the number of subjects n required to determine a proportion p with a precision e with a two-sided α first-type error is the following:

$$n = \frac{p \times (1-p) \times z_{1-\alpha/2}^2}{e^2} \quad (1)$$

Based on this sample, and considering a confidence interval of 95%, in order to be able to determine any percentage with a precision of at least $\pm 5\%$, 384 subjects will be necessary. This corresponds to a hypothetical proportion of 50% which is generally considered acceptable as it yields to the largest sample size for each precision level. Respectively, a precision of at least $\pm 3\%$ or $\pm 10\%$ would necessitate a sample size of 1066 or 97 dulaglutide initiated patients.

In this study, assuming that we would like to be able to describe any proportion with a precision of at least 10% in each country, a minimum sample size of 100 cases is required for any of the countries. Assuming we want that the smallest country to represent at least 10% of the whole sample, it was pragmatically decided to start the study when data on 1,000 initiations of dulaglutide are available in the considered databases with at least 100 cases available in the smallest contributing country.

9.5.2. Feasibility Assessment

Some other characteristics of candidate databases along with current counts of physicians diabetic patients, as well as those treated with GLP-1 receptor agonists is presented below ([Table 9.5.2-1](#)).

Table 9.5.2-1. Database Characteristics and Patient Numbers

Database description	France (DA)	Germany (DA)	Spain (SIDIAP)	Sweden (NPR and SPDR)	The UK (CPRD)
Size of the panel (number of physicians or practices)	1,100 GPs	1,409 PCPs	274 practices	All patients according to inclusion criteria	683 PCPs
Data available since	1997	1992	2000 – 2006§	2005 (1997)	1994
Data lag time	1 month	6 weeks	1 year (data provided in May)	6 months	
Pharmacy information	not available	not available	available	available	not available
Number of patients treated with an anti-diabetic treatment / with diabetes	61,591	96,947 in 2013 / 159,014 last 5 years	23,000 treated for T2DM in 2013	Ca. 400,000	16,479 newly-diagnosed patients in 2014
Number of patients treated with GLP-1 RAs	2,462	2,873 in 2013 / 5,457 last 5 years	About 3,500 in 2013	Ca. 12,000	1,877 new users in 2014; total: 8,010 patients

Abbreviations: CPRD= Clinical Practice Research Datalink ; DA= Disease Analyzer; GLP-1 RA= glucagon-like peptide-1 receptor agonists; GP= general practitioner; NPR= National Prescription Registry; PCP= SIDIAP= The Information System for the Development of Research in Primary Care; SPDR= Swedish prescribed drug register; T2DM= type 2 diabetes mellitus.

* information available for reimbursed drugs

§ depending on the source

More specific feasibility analyses will be conducted to determine whether the data sources capture sufficient exposure to dulaglutide, allowing the DUS to start. Each database being considered will be checked on the following aspects:

- The number of eligible patients (treated with dulaglutide with 6 months baseline data prior to the first observed/recorded prescription)
- The availability and validity of each variable of interest.

The feasibility assessment will help to choose the three countries to be involved in the study, and it will also provide information for the start of data collection.

The timing and frequency of the feasibility analyses will be determined by IMS and Lilly, with the anticipation that it will take place at a maximum of twice every 12 months, in each country.

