9.1. Study Design

This is a multi-country, multi-source, cross-sectional, descriptive study using longitudinal data collected from European EHR databases.

Several countries will be selected from the databases under consideration (France, Germany, Spain, Sweden, and the UK). The justification of the selected countries will be based on the feasibility assessment results (Section 9.5.2) and the market uptake and volume of dulaglutide in each country.

Study period

The study will be conducted for at least three years post launch of dulaglutide (January 2015). The analyses and reporting will commence approximately one year after the launch of dulaglutide, as soon as the data on 1000 initiations of dulaglutide are available in the databases with at least 100 cases available in the smallest contributing country.

Three waves of data extraction/collection and analysis will be performed within at least three years, based on launch projections:

- 1st wave: Q3 2016 (covering patients having initiated the drug from Q1 to Q4 2015)
- 2nd wave: Q2 2017 (covering patients having initiated the drug from Q1 to Q4 2016)
- 3rd wave: Q2 2018 (covering patients having initiated the drug from Q1 to Q4 2017)

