9.3. Variables

Regardless of the coding system used in the database, different populations and subgroups of interest are defined as follows:

Treatment initiation with dulaglutide:

- any record of prescription of dulaglutide during the observation period without prior record of prescription of the same product in the available patient's history
- if no prior history is available to check the above criteria, the prescription is not considered as an initiation

Patients presenting with T2DM:

- with any recorded diagnosis code for T2DM
- or with any recorded treatment code for an ADM other than insulin
- or, with any recorded treatment code for insulin initiated at age >30 (defined as no record of insulin therapy during 6 months prior to first record of insulin treatment)
- or with any record of unspecified diabetes mellitus diagnosis at age >30 and without history of insulin therapy (defined as no record of insulin therapy during 6 months prior to first record of diabetes diagnosis),
- a sensitivity analysis will be conducted to determine the age threshold mentioned above (see section 9.7.3 Sensitivity analysis).

Patients with severe renal failure:

- with a recorded diagnosis of severe renal failure
- or with a recorded glomerular filtration rate (eGFR) value <30 ml/min/1.73 m²

Patients with hepatic disease:

- with a recorded diagnosis of any hepatic disorder

Patients with heart failure:

- with a recorded diagnosis of heart failure

Patients with severe gastrointestinal disease:

- with a recorded diagnosis of any of the following conditions:
 - cancer of the gastrointestinal tract,
 - diseases of the oesophagus,
 - active ulcer at the time of drug initiation (gastric, duodenal, gastro-jejunal, peptic ulcer of unspecified site),
 - active haemorrhagic gastritis, chronic atrophic gastritis, adult hypertrophic pyloric stenosis, obstruction of duodenum, and other motility disorders,
 - digestive fistula,
 - Crohn's disease, ulcerative colitis,
 - diverticular disease of the intestine,
 - severe vomiting, severe diarrhoea and severe constipation
 - motility disorders, including ileus, gastroparesis, et cetera,
 - infectious and inflammatory situations (appendicitis, cholecystitis, cholangitis).

Children and adolescents:

- Age < 18 at the time of treatment initiation
(subgroups of analysis: 0-4, 5-9, 10-14, and 15-17 years old).

Elderly:

- Age \geq 75 at the time of treatment initiation.

Pregnant and breastfeeding women:

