9.7. Data Analysis

9.7.1. General Statistical Considerations

The analysis will be performed per country, on the overall data set of eligible patients and per subpopulations.

Data coming from different databases/countries will not be pooled due to the difference between structure of panels of health care professionals who contribute the data, asynchronicity of databases, heterogeneity in data structure, coding, and prescribing practices. The analysis will be done per year, and will not be cumulative. Thus data coming from different years will not be pooled either.

The statistical analysis will be descriptive including standard univariate analysis; no inferential statistical analyses will be conducted. Continuous variables will be described by the number of available values, mean, standard deviation, median, Q1, Q3, minimum and maximum. Data not available in the databases will be reported as missing. Categorical variables will be described as the total number of available values and relative percentage per subgroup of interest. When relevant, 95% confidence intervals will be calculated for the endpoints.

The statistical analysis will be conducted using the SAS[®] software V9.2 or later on Windows[™] (SAS Institute, North Carolina, USA).

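### The Q2 extraction dates for waves 2 and 3 are not reconciled with the Swedish and SIDIAP data lags, so a yearly cohort can be cut short and no wave as written recovers the missed initiators

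*Protocol*

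**What the plan says.** Section 9.1 of the protocol (Study period) gives one extraction quarter per wave, with no distinction by database. The entry for the second reads "2nd wave: Q2 2017 (covering patients having initiated the drug from Q1 to Q4 2016". Wave 3 repeats that pattern one year on, with a Q2 2018 extraction for the 2017 cohort. Wave 1 allows a quarter more, with a Q3 2016 extraction for the 2015 cohort.

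Table 9.5.2-1 gives the data lag as 1 month for France, 6 weeks for Germany, 6 months for Sweden and, for SIDIAP, "1 year (data provided in May". The UK cell is empty. Section 9.4.3 adds that the Swedish registers are "updated at least quarterly".

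Two rules decide what happens to a patient who is not yet visible at extraction. Section 9.7.1 states: "The analysis will be done per year, and will not be cumulative. Thus data coming from different years will not be pooled either". Section 9.3 defines an initiation as a dulaglutide prescription "without prior record of prescription of the same product in the available patient's history".

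The medication-error measure in Section 9.3 needs the interval to the next prescription. Section 9.9.1 treats a next prescription that has not yet been captured as missing for that measure.

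The protocol nowhere sets the wave dates against the lags, and it describes no re-extraction of an earlier year.

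**The concern.** A wave can describe a full calendar year only if the data held at extraction reach 31 December of that year. An extraction in Q2 falls three to six months after year-end, while the stated Swedish lag is six months and the SIDIAP lag may be twelve. Where the lag exceeds the gap, the table labelled as a full year covers only its earlier part.

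Three things are at stake. First, counts of initiators in the affected country are understated. Second, country tables for the same nominal year cover different parts of it; within Sweden, wave 1 would be complete while waves 2 and 3 might not be, which distorts any year-to-year reading. Third, initiators close to the cut-off have little or no time to receive a second prescription, so missing data for medication errors would concentrate among them.

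The patients concerned are not picked up later. Someone who started in November 2016 already has a dulaglutide record and does not qualify as a 2017 initiator in wave 3.

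**Working it through.** **Inputs.** Extraction quarters and target years come from Section 9.1; lags come from Table 9.5.2-1. The plan's implied figure is 100% coverage of each target year, since every wave is said to run from Q1 to Q4.

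**Formula.** Cut-off = extraction date minus lag. Coverage = days of the target year up to and including the cut-off, divided by days in that year, with a ceiling of 100%. Each is evaluated on the first and last day of the extraction quarter. If starts are uniform over the year, coverage is also the share of initiators seen.

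**Where the plan's figure is reproduced.** France (1 month) and Germany (6 weeks) reach 100% in all three waves. Their earliest wave 2 cut-offs are 1 March and 18 February 2017, both after year-end. Sweden reaches 100% in wave 1: Q3 2016 minus 6 months gives 1 January to 30 March 2016. The UK cannot be checked because no lag is given.

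**Where it is not reproduced.**

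| Database and wave | Cut-off range | Days covered | Coverage |
|---|---|---|---|
| Sweden, wave 2 (2016) | 1 Oct to 30 Dec 2016 | 275/366 to 365/366 | 75.1% to 99.7% |
| Sweden, wave 3 (2017) | 1 Oct to 30 Dec 2017 | 274/365 to 364/365 | 75.1% to 99.7% |
| SIDIAP, literal 12 months, wave 1 (2015) | 1 Jul to 30 Sep 2015 | 182/365 to 273/365 | 49.9% to 74.8% |
| SIDIAP, literal 12 months, wave 2 (2016) | 1 Apr to 30 Jun 2016 | 92/366 to 182/366 | 25.1% to 49.7% |
| SIDIAP, literal 12 months, wave 3 (2017) | 1 Apr to 30 Jun 2017 | 91/365 to 181/365 | 24.9% to 49.6% |

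If the literal 12 months is counted back from a May delivery, SIDIAP coverage is about 33% to 41% in every wave, including wave 1.

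**Alternative SIDIAP reading.** If the May delivery holds the whole previous calendar year, coverage is 100% in every wave, provided extraction follows the delivery. Q2 opens on 1 April, so an extraction before the May delivery would not have that year.

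**Time for a next prescription.** In Sweden, an extraction on 30 June has a cut-off of 30 December. A patient starting in the last days of December then has no follow-up, and one starting on 1 October has at most about three months.

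**Earliest date for a complete year of initiations.** Sweden: 31 December + 6 months = 30 June of the following year. SIDIAP, literal reading: 31 December + 12 months = 31 December of the following year, in practice the May delivery after that (May 2017 for 2015, May 2018 for 2016, May 2019 for 2017).

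**The case against.** The case against has several good parts.

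- **Sweden can be met within the plan.** Section 9.1 says only Q2, and an extraction on the last day of June misses a single day. A reader might infer that the Swedish year cannot be covered at all; the documents do not support that. What stands is that most of the quarter falls short, and that even the last day leaves late-December starters without follow-up. Regular register updates do not help, because update frequency is a different thing from lag.
- **The SIDIAP cell has a benign reading.** A note about delivery in May sits oddly with a rolling 12-month lag, and May falls in Q2. This stands: the large shortfalls hold only on the literal reading.
- **Dates are provisional.** The milestones text in Section 4 calls them estimates that may change with feasibility and with data capture in each country, and Section 9.1 ties the waves to launch projections. Section 9.7.1 acknowledges that databases are not synchronous, and Section 9.7.5 leaves variation between countries to the SAP. This lowers the severity. However, the feasibility checks listed in Section 9.5.2 are patient numbers and the availability and validity of variables. Completeness of the initiation year is not among them.
- **Loss need not be permanent.** A reader might infer from the non-cumulative rule that missed patients are gone for good. That rule governs the analysis and does not forbid extracting a year again, and data collection runs to Q2 2019. What stands is that no such step is written.
- **Reach is limited.** Three of the five countries will be chosen, and Table 9.3.2-1 names Spain only as an alternative. Sweden is in the first-named set and heads the mock table in Section 9.7.4.

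A reader might also scale the loss up by assuming that starts rise through each year, or infer that subgroup shares are biased. The protocol gives no monthly starts and nothing on how late initiators differ, so neither can be sized.

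**Conclusion.** The point holds as a mismatch between the wave dates and the stated lags that should be corrected before data collection. In Sweden, waves 2 and 3 leave 0-25% of the target year uncovered, depending on the day in Q2 and assuming uniform starts, and late-year initiators contribute little or nothing to the medication-error measure. In SIDIAP, the size depends on what the lag entry means: 50-75% of the year uncovered in waves 2-3 and 25-50% in wave 1 on a literal 12-month lag, or nothing if the May delivery holds the full previous calendar year and extraction follows it. France and Germany are unaffected.

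As written, no later wave recovers the missed initiators. This rests on the dates being followed as stated and on no re-extraction being added; the protocol permits both to change. The SIDIAP part applies only if Spain is selected.

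**What to change.** 1. Replace the common extraction quarter in Section 9.1 by a rule per database: 31 December of the initiation year, plus that database's lag, plus a short allowance for the next prescription. The protocol gives no figure for the allowance. If 1 to 3 months is assumed, the Swedish date falls between 31 July and 30 September, that is, Q3 instead of Q2. This still precedes the Q4 interim reports, and wave 1 already runs from a Q3 extraction to a Q4 report.
2. State the SIDIAP data cut-off at each delivery. If the May delivery holds the full previous calendar year, require extraction after it.
3. If the literal 12-month lag applies, label the SIDIAP interim tables as partial-year and re-extract each earlier year from a later May delivery, still reported by year. The last would be May 2019 for the 2017 cohort, within the Q2 2019 end of data collection and before the final report in Q4 2019. Its cut-off in May 2018 also leaves at least four months after year-end for a next prescription.

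**Cost.** Protocol wording, and a Swedish extraction about one quarter later. If SIDIAP is used under the literal lag, some programs are re-run and its full-year tables come later: the complete 2016 cohort would not be available for the interim report planned for Q4 2017.
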